All adverse events (AEs) recorded on the adverse event form and will be sent to the Principal Investigator (PI) within 72 hours of the event. AEs will be reported to the IRB according to the IRB policies and procedures. Any unanticipated problems involving risk to the participants or others will be discussed with the Principal Investigator (PI).

Serious Adverse Event Reporting

All SAEs will be recorded on the adverse event case report form and will be reported to the Principal Investigator within 24 hours after becoming aware of their occurrence. All SAEs will be reported to the IRB and FDA in accordance with applicable regulations and policies. Our procedures for reporting the serious adverse events will be as follows: 1. SAEs will be recorded in the patient's study chart and reported to the Principal Investigator within 24 hours of the study team's awareness of the occurrence by email or text message and will be reported to Vanderbilt's IRB according to IRB policies (5 working days). The Study Coordinator will report the event within 5 business days to the Safety Monitor who will be responsible for systematically reviewing SAEs, assigning causality, and evaluating relatedness of each event. The Principal Investigator will have the opportunity to review and agree (or not) with the Safety Monitor's determination on each event. When the Safety Monitor suspects an event is study-related, he/she will have the opportunity (if he/she chooses) to access additional data in order to conduct appropriate safety monitoring. The Safety Monitor will determine if any necessary actions need to occur as result of the event in order to increase the safety of the protocol.

Safety Stopping Criteria:

The trigeminal block procedure is standard of care in the pain clinic. Expected effects of successful block include transient numbness, transient facial weakness including ipsilateral eyelid lag, and rare visual changes all of which resolve with the resolution of the effects of lidocaine over the typical course of 2 hours. Rare risks of the block procedure include infection, bleeding, nerve injury from the mechanical placement of the block needle. Rare risks of using lidocaine during the block procedure include intravascular or subdural injection resulting in transient unresponsiveness and/or seizure, mild sedation, bradycardia, and arrhythmias. These rare risks and side-effects must be differentiated from potential side-effects due to the addition of guanfacine. As all eligible patients are in

clinic for diagnostic nerve block as standard of care, they will receive clinical consent to treatment for the injection procedure itself and necessary x-ray radiation as part of routine care.

Common side-effects of daily oral use of guanfacine include dizziness, drowsiness, tiredness, low blood pressure, and slow heart rate. These side-effects are similar among other medications in the same class including clonidine, dexmedetomidine, tizanidine. Clonidine is also used as an intrathecal analgesic and as a perineural adjunctive injectate for regional blocks. We would expect that the side-effects of guanfacine as an adjunct to lidocaine block might additionally include increased dizziness, drowsiness, tiredness, low blood pressure, and slow heart rate. If the level of sedation experienced by at least 20% of patients in either group is greater than anticipated either by severity or duration, study enrollment will be stopped and the safety monitor engaged for an interim review of data comparing the study groups. If oversedation is occurring in only one group, an adjustment will be made to maintain monitoring for more than an hour (as is standard) until complete recovery.

Potential adverse events (AE) including any occurrence of the above listed procedural or medicine-related side-effects and risks will be documented as AE's, described and categorized as mild-, moderate-, severe- AE and submitted for review by the safety monitor and IRB. The PI will also submit the likelihood of the AE being potentially related to the use of guanfacine. Severe AEs would include the occurrence of a seizure, severe sedation requiring ventilation support; bradycardia, unstable arrhythmias, or hypotension requiring resuscitation (medical or mechanical). The occurrence of a severe AE that is deemed study related would result in a stop of enrollment to report the data to the IRB, and FDA guidance would be obtained prior to study restart.

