2.0 STUDY DESIGN

Primary Hypothesis:

Due to its different but relevant mechanism of action, guanfacine will be an effective adjunct to lidocaine in trigeminal nerve block for the treatment of painful trigeminal neuropathy by enhancing and prolonging pain relief compared to lidocaine alone.

Endpoints

The following endpoints will be measured to evaluate the exploratory objectives of the study assessing guanfacine and lidocaine in combination compared to lidocaine alone, in pain management in the painful trigeminal neuropathy patient.

- Primary endpoint: time to return to baseline pain (VAS) measurement after treatment with guanfacine as adjuvant to 1% lidocaine compared to 1% lidocaine alone
- Safety endpoint: comparable side effect profile of combination product compared to lidocaine alone on relevant adverse event measures: sedation, local site reaction, confusion
- Secondary endpoint: pain intensity after treatment to be measured throughout the follow-up periods on a visual analog scale (VAS)
- Secondary endpoint: quality of life after treatment to be measured using PROMIS Global Health -10 SF during the follow-up periods
- Secondary endpoint: frequency of acute trigeminal nerve pain attacks during the follow-up periods
- Secondary endpoint: total amount of rescue medications (opioid and non-opioid analgesics) for pain management during the follow-up periods
- Secondary endpoint: time to first rescue medication during the follow-up periods

Experimental Design

The trial is designed as a single-center, randomized, double-blind, controlle, 2x2 crossover pilot study with two arms: study drug (guanfacine and lidocaine combination) and active control (lidocaine alone). The target sample size is 30 study drug vs. 30 active control.

Not all participants that are randomized and initiate the first arm of the trial will *necessarily* complete *both* arms of the crossover trial. Based on previous experience, initiating the first arm of the cross over trial in 40 participants should be sufficient reach the full sample size (30 study drug vs. 30 active control). The trial will be complete and enrollment will cease upon reaching the full proposed sample size (30 study drug vs. 30 active control).

Approximately 80 patients meeting preliminary enrollment criteria will be consented for screening with the goal of roughly half being eligible to randomize and begin participation in the trial.

Inclusion Criteria

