5.0 STUDY PROCEDURE

The study is a single center, randomized, double-blind, 2 x 2 crossover pilot study with two arms; study drug (guanfacine and lidocaine combination) and active control (lidocaine alone). Adult participants between 18 and 80 years of age who have been diagnosed with painful trigeminal neuropathy will be consented for the study. The study includes three visits; an initial visit for evaluation, consent, and baseline surveys followed by two procedural visits. After each procedural visit data will be collected for 14 days. Participants will be randomized in permuted pairs (to ensure balance after every second enrollment) to receive either study drug (guanfacine and lidocaine combination) or active control (lidocaine alone) for the first nerve block procedure. Following the first procedural visit and 14-day follow up period, the study team will assess inclusion and exclusion criteria and (if eligible) schedule the second procedural visit.

Assessment	Study Visit 1: Consent and screening (Day -15 to 0)	Study Visit 2: Procedure 1 (Day 1)	Follow-up period 1 (Day 2-14)	Study Visit 3: Procedure 2 (≥15 days after procedure 1)	Follow-up period 2 (14 days after procedure 2)
		Administrative P	rocedures		
Eligibility Review	X	X		X	
Informed Consent	X				
Demographics	X				
Pain History	X				
Baseline Pain	X	X	X	X	X
Medical History	X				
Concomitant Medications	X	X		X	
Surgical/ Past Treatments History	X				
Verbal Pregnancy Screen	X				
PROMIS Global 10- SF	X	X	X \$	X	X \$
Pain Interference	X	X		X	
Pain Intensity (VAS Score)	X	X #	X %	X #	X
Frequency of Attacks	X	X	X \$	X	X \$
Rescue Medications		X %	X %	X %	X
Randomization	X				
	Cl	inical Procedures/	Assessments		•
Physical Exam (general)	X	X		X	
Physical Exam (pain)	X				
Vitals (HR, RR, Temp, BP)	X	X		X	
Height/ Weight	X				
12-Lead ECG ^	X				
Continuous ECG monitoring		X		X	
Nerve Block Administration		X		X *	
Imaging MRI/ CT report +	X				
Adverse Events		X	X	X	X
		Laboratory Pro	cedures		
Urine Pregnancy Test		X		X	
Urine Drug Screen	X				

^{#:} Collected every 30 minutes for 8 hours by text message (REDCap) or patient diary

^{%:} Collected daily for up to 28 days by text message (REDCap) or patient diary

Collected weekly for up to 4 weeks by study nurse phone call

If pain score >5

^{+:} Review recent imagining, if not available then order as standard of care
^: Order 12-lead ECG as standard of care if one not available within 2 months of screening visit

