Study Visit 1: Consent and Screening (Day -15 to Day 0)

Patients with facial pain will be evaluated in clinic; those deemed to have a diagnosis of painful trigeminal neuropathy will be considered for enrollment. Informed consent will be obtained prior to collecting data. Those patients that meet eligibility (inclusion/exclusion criteria outlined above) will be introduced to the study. Consented patients will become enrolled as study participants and will complete baseline measurement prior to randomization. Baseline data that will be collected includes demographics (name, age, sex), physical examination; heart rate and rhythm, blood pressure; comorbid health conditions and prior surgeries or treatments; current and past medications within 6 months. [name] will order an EKG if the participant has not had one within the past 2 months prior to the visit, as part of standard care. The targeted pain history will include pain duration, frequency of exacerbations, location, radiation, severity (VAS), quality, instigating event, exacerbations, alleviations, pain treatment frequency and duration of use (non-medical and medical treatments) and changes in pain over time. The targeted pain physical exam will include assessment of light touch test for allodynia and pinprick test for hyperalgesia of the trigeminal dermatome V1-3 regions of the face. Standard practice prior to trigeminal nerve block is to review recent MRI or CT imaging to ensure safety of needle approach to target location. If no recent imaging exists, this will be ordered as part of standard care prior to nerve block. Participants will be asked if there is a possibility they are pregnant. Women of childbearing potential will be educated on birth control methods and will agree to 2 methods of birth control that they will plan to use during the study period (abstinence is an appropriate method). A urine drug screen for illicit use of controlled substances will be obtained. Patient-reported outcome forms to be completed include the PROMIS Global-10 SF and Pain Interference forms. Current and average 24-hour pain (VAS) before procedure will also be recorded. Assessments will be recorded according to the patient's preference, either on paper or via electronic forms using REDCap. All data will be entered into REDCap.

Study Visit 2: Procedure 1 (Day 1)

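### The severe-AE stop rule halts enrollment but does not say that pending blocks of participants already enrolled are held

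*Combined protocol and SAP*

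**What the plan says.** The severe-AE rule is in section 7.0, Safety Stopping Criteria: "The occurrence of a severe AE that is deemed study related would result in a stop of enrollment". The data go to the IRB, and "FDA guidance would be obtained prior to study restart". The examples given are seizure, sedation needing ventilation support, and bradycardia, unstable arrhythmia or hypotension needing resuscitation. They are introduced as inclusions, so the list is open.

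The same subsection has a sedation rule. If at least 20% of patients in either group have more sedation than anticipated, "study enrollment will be stopped and the safety monitor engaged for an interim review". If only one group is oversedated, post-block monitoring is extended beyond the standard hour.

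On timing, section 5.0 (Study Visit 1) states: "Consented patients will become enrolled as study participants and will complete baseline measurement prior to randomization". The schedule in section 5.0 places consent and randomization at Visit 1 (Day -15 to 0), block 1 on Day 1, and block 2 at least 15 days after block 1. After the first follow-up period, "the study team will assess inclusion and exclusion criteria and (if eligible) schedule the second procedural visit".

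On causality, section 7.0 has the PI grade each SAE as not, possibly or probably related to study drug. Its paragraph on SAE reporting also makes the Safety Monitor responsible for assigning causality, and the PI may agree or disagree. The PI is told of an SAE within 24 hours, the Safety Monitor within 5 business days.

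**The concern.** A stop rule is meant to prevent further exposure while an event is assessed. Stopping enrollment nearly does that when dosing follows enrollment at once. Here an enrolled participant may have two blocks still to come. Each participant is meant to receive guanfacine once, and in the lidocaine-first order this happens at block 2. If the severe-AE rule is followed to the letter, an enrolled participant could be given guanfacine after a related seizure or resuscitation in someone else, while FDA guidance is still awaited. What is at stake is participant safety. The primary analysis is not affected.

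**Working it through.** The plan gives no figure on this point to reproduce. The check is mainly of the text, with one piece of arithmetic for scale.

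**1. Does enrollment precede dosing on every reading?** Section 5.0 uses the word for consented patients (Study Visit 1) and also for randomization: "Participants will be randomized in permuted pairs (to ensure balance after every second enrollment". The schedule puts both at Visit 1. On either meaning, enrollment is complete before block 1 and well before block 2.

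**2. Does anything else hold a pending block?**

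| Provision | What it does | Study-wide hold stated? |
|---|---|---|
| Eligibility review at Visits 2 and 3 (section 5.0) | Applies the individual criteria of section 2.0 | No; no criterion refers to a study-level stop |
| Default for block 2 (sections 5.0 and 9.1) | Both treatments intended unless that participant has intolerable toxicity | No |
| Withdrawal (section 8.0) | Subject withdrawn if the PI considers participation harmful to that subject | No; per subject |
| Safety Monitor actions (section 7.0, SAE reporting) | Safety Monitor decides whether any action is needed | No; discretionary |
| Restart clause (section 7.0, Safety Stopping Criteria) | FDA guidance needed first | Implied only |

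**3. How much guanfacine exposure comes at block 2?** Section 2.0 says "initiating the first arm of the cross over trial in 40 participants should be sufficient". Permuted pairs give 20 per order. With p the fraction reaching block 2, guanfacine doses = 20 (block 1) + 20p (block 2).

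- p = 0.50, the minimum that gives 30 per arm (20 + 20p = 30): 10 of 30 = 33%.
- p = 0.75 (30 completers in section 9.1, of 40 starters): 15 of 35 = 43%.
- p = 1: 20 of 40 = 50%.

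**4. How many doses would be pending at a stop?** The documents give no accrual rate, so this is illustration only. Assume r eligible starters per 30 days, a days from enrollment to block 1, and b days between blocks. Pending guanfacine doses are G = (r·a/30)(0.5 + 0.5p) + (r·b/30)(0.5p).

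- a = b = 15, p = 0.75, r = 2: 1 × 0.875 + 1 × 0.375 = 1.25. With r = 1 it is 0.625, and with r = 4 it is 2.5.
- Lowest case (r = 1, a = 7, b = 15, p = 0.5): 0.175 + 0.125 = 0.30.
- Highest case (r = 4, a = 15, b = 28, p = 1): 2 + 1.87 = 3.87.

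Only eligible starters are counted, since section 2.0 consents patients "with the goal of roughly half being eligible to randomize and begin participation in the trial".

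**5. Is the trigger tied to the causality scale?** The rule does not say which level counts as related, or whose view prevails if the PI and Safety Monitor differ. The scale rates relation to study drug, whereas the rule speaks of relation to the study.

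**The case against.** The strongest reply is that a full pause was plainly meant. A study cannot restart unless it has stopped. Section 2.0 also uses enrollment loosely, pairing its end with completion of the trial. Withdrawal under section 8.0 is mandatory once the PI sees a risk of harm. Section 6.0 adds real-time AE monitoring and an anesthesiologist present throughout care. With the PI told of an SAE within 24 hours, a hold is likely in practice. All of this stands as context, and it means that a reader should not infer that the investigators plan to keep dosing after a severe related event. It does not supply the missing statement: each safeguard is discretionary, per subject or implied.

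A reader might also infer that the sedation rule needs the same hold. The documents do not support that. The rule provides an interim review, and its extended-monitoring step presupposes further blocks, which is a reasonable, proportionate choice for sedation. Its 20% trigger has no minimum denominator, so 1 patient among the first 5 in a group would meet it; attaching a full dosing hold to that would be heavy.

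It is fair, too, that *related* on a three-level scale most naturally covers both *possibly* and *probably*. The missing level and tie-break are drafting details, worth settling in the same sentence but not a separate fault.

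Finally, the pending-dose counts carry little weight. In the 1.25 case, 0.375 (30%) belongs to lidocaine-first participants who have not yet had block 1, so their guanfacine is at least 15 days beyond that block and follows another eligibility review.

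**Conclusion.** The point holds for the severe-AE rule. Its stated action falls on a step that, in this crossover, lies before both blocks, and no section says that pending blocks are held. It ranks between a minor clarification and a recommended change: the intention is probably sound, the events concerned are grave, and the correction is short.

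The share of guanfacine doses given as second blocks (33% to 50%) follows from the plan's 40 starters and paired randomization, for p from 0.50 to 1. The pending count (0.3 to 3.9) rests on assumed accrual and waiting times, and counts doses outstanding, not doses predicted to be given. No risk of harm per dose can be derived from the documents.

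**What to change.** Amend the severe-AE sentence in section 7.0, Safety Stopping Criteria, to say that:

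- the trigger is any severe AE, not only the listed examples, considered at least possibly related to study drug or block procedure by either the PI or the Safety Monitor. Limiting it to the listed events would leave out, for example, stroke, which section 6.0 names as a risk;
- it suspends enrollment, randomization and all pending first and second study blocks until the IRB report has been made and FDA guidance obtained;
- follow-up of participants already dosed continues;
- the Safety Monitor is told of such events within 24 hours, as the PI is for SAEs.

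Leave the sedation rule as written.

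Cost: a wording amendment, with no change to endpoints, sample size or analysis. In operation, expect occasional pauses, delayed second blocks, re-screening of participants whose 15-day screening window lapses during a hold, and possible replacement of participants lost while waiting. The general severity grading in section 7.0 calls an event severe if it prevents usual activities, so an explicit *possibly related* threshold may fire more often than the listed examples suggest. The interval between blocks has a minimum of 15 days and no maximum, so a hold preserves the crossover.

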8.0 STUDY WITHDRAWAL/DISCONTINUATION

Participants will be advised that they have the right to withdraw from the study at any point in time for any reason. During the study, if the participants no longer wants to participate, they will be withdrawn from the study. Contact information for the PI and study staff will be made available to the participant upon enrollment in the consent document.

Subjects will be withdrawn from the study if the PI's medical judgment is that participation places the subject at risk for harm.

[figure not shown]
9.0 STATISTICAL CONSIDERATIONS

The effects of guanfacine adjuvant (intervention) versus active control on the time to return to baseline pain (primary) will be assessed using linear mixed-effects regression, adjusting for randomization order group and its interaction with the intervention/control indicator. A random intercept indexed by study participant will be used to account for within-participant correlation of the pre- and post-crossover measurements. The linear model assumptions will be assessed by examining residuals, conditional on the empirical Bayes estimates of random effects. If there is evidence that the linear model assumptions are violated (e.g., non-normal residuals or the very unlikely possibility of right censoring), alternative model formulations will be considered as necessary. The overall effect of intervention on the primary outcome will be tested using a two degree-of-freedom chunk test against the null hypothesis of no intervention main effect and no order-by-intervention interaction. The effects of intervention on the mean time to return to baseline will be summarized using estimates and 95% confidence intervals, stratified by order group. The effects of guanfacine adjuvant versus active control on secondary outcomes will be assessed using similar mixed-effects regression techniques as appropriate for the type of outcome (including proportional hazards, cumulative logit, logistic, and linear regression methods), adjusting for

randomization order group and its interaction with the intervention/control indicator. A random intercept indexed by study participant will be used to account for within-participant correlation. Quantitative and/or graphical regression diagnostics will be examined, and alternative model formulations will be considered as appropriate. Intervention effects will be tested and summarized as described above. No familywise hypotheses will be tested; no adjustments will be made to control any familywise type-I error probability. The type-I error rate will be fixed at 5%. All statistical analyses will be implemented in R (www.r-project.org; latest version) and the add-on package "lme4" and other packages as necessary.

9.1 Statistical power and sample size. Evidence from the medical literature and expert opinion suggests that the mean duration of pain relief after treatment with lidocaine alone (active control group) is approximately 140

minutes. The sample size for the proposed study was selected to achieve at least 80% power to detect a 20% or greater increase in the duration of pain relief after treatment with lidocaine plus guanfacine as an adjuvant (treatment group). This corresponds to a mean difference of 28 minutes. Again, although this degree of difference is not likely to be clinically meaningful, we are conducting this trial as a proof of mechanism only. If successful, we would pursue a modified formulation of guanfacine such that delivery was extended and pain relief duration was considerably longer. A simulationbased power analysis was implemented using linear mixed-effects regression as described above. Both betweenand within-subjects variability conservatively assumed to have standard deviation 30

minutes. Under these conditions, 30 participants will ensure approximately 90% power to detect a significant mean difference (28 minutes or greater in pain relief duration). **Figure 2** illustrates the estimated statistical power for somewhat larger and smaller effect sizes (i.e., 15%, 20%, and 25% increase in pain relief duration), for a variety of sample sizes.

Dropout and intent-to-treat: If VAS < 5 on the pain scale, participants will not be eligible for second trigeminal nerve block during the visit. Study nurse will continue monitoring the participant's pain intensity daily (days 15-28) to monitor when the participant pain is above 5 on the pain scale and eligible for the second block. In general, the study intends that participants would receive both treatments unless they experience intolerable toxicity. If a participant is unable or ineligible to receive second trigeminal nerve block, then the participant's data collected during the first nerve block will be included in the final analysis. In addition, a replacement participant will be enrolled so that the minimum number of 30 for each arm is reached. An exploratory analysis will be done post-hoc to evaluate any differential progress to second block between the initial randomized groups. Approximately 70 people with painful trigeminal neuropathy will be evaluated at Vanderbilt University Medical Center to determine if they are eligible to take part in this study. We expect to consent 70 subjects with 30 completing the full study.

Although 28-70 incremental/additional minutes of pain relief would be clinically significant by itself, the study finding would validate the pain relief mechanism of guanfacine in the trigeminal nerve and show that enhanced pain relief can be achieved by the combination of drugs, and therefore extends the utility of the mechanism into further clinical development.

